juvenile idiopathic arthritis (pcJIA). For RA, PsA and pcJIA patients, use of tofacitinib in combination with biologic DMARDs or potent immunosuppressants such as azathioprine and cyclosporine is not recommended. Additionally, for RA and PsA patients, only the 5 mg twice daily and 11 mg once daily dosing regimens are approved; the 10 mg twice daily and 22 mg once daily dosing regimens are not indicated for use in non-UC patients. For pcJIA patients, only the 5 mg twice daily dosing regimen is approved. Due to the potential for off-label use of the 10 mg twice daily and 22 mg once daily dosing regimens in non-UC patients, as well as the potential for use of tofacitinib in non-indicated populations, it would be useful to understand the patterns of post-approval use in the US.

In addition, understanding of long-term safety associated with real-world tofacitinib use, including the potential risk of malignancy and other safety events of interest, is needed. Follow up of large cohorts of patients over a long period can help in the evaluation of any potential risk of malignancy, as well as other potential safety events of interest that may be associated with tofacitinib treatment. It is important that surveillance also examines patient co-morbidities which may influence the occurrence of safety events, as well as mortality. Active surveillance studies help assess the risk of safety events of interest overall and within strata of disease severity, treatment history, patient co-morbidities or risk factors and other concomitant therapy.

To understand the patterns of tofacitinib use in the US, as well as to characterize the risk of safety events of interest that may be associated with its use, a non-interventional, drug utilization and active surveillance study will be conducted using data from the International Business Machines (IBM) Watson Health MarketScan® Research Databases. This non-interventional study is designated as a Post-Authorization Safety Study (PASS) and is a post-marketing commitment to the US Food and Drug Administration (FDA). It is also a category 3 study in the tofacitinib European Union (EU) risk management plan (RMP).

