8. RESEARCH QUESTIONS AND OBJECTIVES

The research questions and associated objectives for this study are as follows:

Research Question 1:

What are the utilization patterns of tofacitinib in the US with regard to on-label and off-label use?

Objectives:

- Estimate the proportion of tofacitinib users who receive the drug for the approved indications during the study period
- Describe the characteristics of patients who are prescribed to facitinib for on-label, off-label and unknown indications in terms of the following:
 - Demographics (e.g., age, sex);

- Comorbidities;
- Prior and concurrent medications;
- Prescribed daily dose and duration of tofacitinib therapy
- Estimate the proportion of UC patients on 5 mg twice daily or 11 mg once daily and 10 mg twice daily or 22 mg once daily maintenance therapies
- Estimate the proportion of non-UC patients on 10 mg twice daily or 22 mg once daily therapy
- Estimate the proportion of patients with approved indications who have ≥1 thrombosis risk factors and are prescribed tofacitinib, overall and stratified by dose
- Estimate the proportion of TNFi-naïve UC patients prescribed tofacitinib pre and post 01 July 2019

Research Question 2:

What are the incidence rates of safety events of interest in adult ulcerative colitis (UC) patients treated with tofacitinib (including the immediate-release formulation [dosed as 5 mg and 10 mg twice daily] and the extended-release formulation [dosed as 11 mg and 22 mg once daily] formulations) in the course of routine clinical care?

Primary Objective:

The primary objective is to estimate the incidence rate of malignancy, excluding non-melanoma skin cancer (NMSC), among adult UC patients who initiate tofacitinib in the course of routine clinical care.

Secondary Objective:

The secondary objective is to estimate the incidence rates of other safety events of interest among adult UC patients who initiate tofacitinib in the course of routine clinical care. These other safety events include (but may not be limited to) the following:

- Lung cancer
- Lymphoma
- NMSC
- Serious infections
- Opportunistic infections (e.g. tuberculosis)
- Herpes zoster (HZ) reactivation
- Major adverse cardiac events (MACE)
- Venous thromboembolism (VTE; deep venous thrombosis [DVT] and pulmonary embolism [PE])
- Myocardial Infarction (MI)
- Hepatic events

- Progressive multifocal leukoencephalopathy (PML)
- Gastrointestinal (GI) perforations
- Interstitial lung disease (ILD)
- Fractures

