9.3.4.2. Active Surveillance Study

For the active surveillance portion of the study, index date will be defined as follows:

Cohort 1: This will be the date of first prescription for tofacitinib since 30 May 2018, following a diagnosis of UC as described in Section 9.2.1.2.1.

Cohort 2: This will be the date of first prescription for a specific biologic agent since 30 May 2018, following diagnosis of UC as described in Section 9.2.1.2.2. For patients with more than one biologic initiation, more than one index date will be defined (e.g., one for each biologic initiation).

Cohort 3: This will be the date of first prescription for a specific immunomodulator/immunosuppressant agent since 30 May 2018, following diagnosis of UC as described in Section 9.2.1.2.3. For patients with more than one immunomodulator/immunosuppressant initiation, more than one index date will be defined.

Cohort 4: This will be the date of UC diagnosis as described in Section 9.2.1.2.4, since 30 May 2018.

[figure not shown]

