9.3.5. Follow-up in the active surveillance population

Patients in the active surveillance population will be followed from index date until first occurrence of each outcome of interest, treatment switch or discontinuation, with the appropriate outcome-specific extension to exposure (i.e. 90 day window for acute events, and "once-exposed always at risk" approach for non-acute events like malignancy as described below), and with death, lost medical/pharmacy coverage, and end of data collection (30 June 2025) treated as censoring events.

Acute events of interest in this study are thought to potentially occur at a higher rate while on drug, but that increased risk subsides after the drug is discontinued (i.e., serious and opportunistic infections, herpes zoster reactivation, MACE, VTE, GI perforation, PML). These events will be evaluated over a risk window that includes time from drug initiation until 90 days after end of treatment. When a patient initiates a new therapy within the 90-day

[figure not shown]
extension, the time and events during the overlapping period will be assigned to both treatments. An example of the as-treated approach with the 90-day extension period is provided in the scenario illustrated below.

------ represents risk period counted
+++++ represents time not included in the risk period
x represents occurrence of an acute safety event of interest such as MACE
) represents drug discontinuation
| represents tofacitinib initiation
| represents biologic initiation
| represents 90-day extension period

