In the above scenario, the patient has two biologic initiations and a tofacitinib initiation. The initiation of tofacitinib therapy occurs within the 90-day extension period for the first biologic. Thus, the time and event during the overlapping period will be assigned to both the first biologic and tofacitinib. Specifically, for the first biologic initiation, a safety event occurred within the 90-day extension period, and exposure time is counted from the time of drug initiation (Index date 1) until the occurrence of the safety event. For the tofacitinib initiation, one safety event occurred and exposure time is counted from Index date 2 (date of initiation of tofacitinib which occurs within the 90-day extension period of the first biologic initiation) to the occurrence of the safety event (which also occurred within the 90-day extension period for the first biologic). Tofacitinib treatment was discontinued when the safety event occurred, and there is a period of time where no treatment is used. For the second biologic initiation, one safety event occurred and exposure time is counted from Index date 3 to the safety event.

For the purpose of analysis, the patient has 2 biologic initiations and a tofacitinib initiation:

A sensitivity analysis whereby if a new medication is started during the 90-day window after discontinuation of a previous medication, initiation of the new medication will stop the 90-day risk window, and any event prior to the new medication start will be assigned to the discontinued medication will also be conducted and further discussed in the SAP. The 90-day extension period is implemented in part to accommodate ongoing exposure to treatments with longer half-lives, and in part to ensure that any subclinical or undiagnosed illness at time of end of treatment is captured. For each patient, follow-up time contributing to one of the three treated cohorts will be calculated as the sum of dispensed medication days (based on days supply) plus the 90-day extension period.

For NMSC and malignancies, surgery for UC, and death (and as a sensitivity analysis for PML), the occurrences of which are expected to be delayed relative to the time of exposure, the outcomes will be evaluated from drug initiation until the first event or loss to follow up, reflecting a "once-exposed always at risk" paradigm. If a patient switches to a new drug, the subsequent observation time will contribute to multiple therapies.

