9.7.2. Analysis of safety endpoints of interest

For the safety endpoints of interest, descriptive statistics, counts and proportions, cumulative incidence proportions, and crude incidence rates (i.e., number of events per person-years) and associated two-sided 95% confidence intervals will be calculated as appropriate. UC patients with a baseline history of an outcome of interest will be excluded from the calculation of the incidence rate for that particular outcome of interest (e.g. patients with a baseline history of malignancy will be excluded from the calculation of the incidence rate for malignancy).

Several subgroup analyses will be performed. These include (but are not limited to) stratification by:

- Tofacitinib dose (5 mg twice daily vs. 11 mg once daily vs. 10 mg twice daily vs. 22 mg once daily)
- Patient characteristics such as age at index date, including a subgroup analysis of patients <50 years vs. ≥50 years, and patients <65 years vs. ≥65 years
- For the outcomes of VTE and MACE, subgroup analysis of patients with ≥1 thrombosis risk factors (as defined in Section 9.3.1.1) vs. no thrombosis risk factors, and
- Key indicators of disease severity such as number of previous biologic treatments (i.e. prior biologic use vs. none; among those with prior biologic use, 1st biologic vs. 2nd biologic vs. ≥3 biologics)

This will be a time to first event analysis based on an index date defined for each cohort with appropriate censoring rules applied (based on therapy switches, end of study, etc.) for those

who do not experience an event by end of follow-up period. Rates will be expressed as the number of events/100 person-years of follow-up.

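### Malignancy is described as delayed but its risk window opens on the day of drug initiation, so the primary rate should be reported beside a lagged rate and rates by time since index

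*Protocol*

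**What the plan says.** Protocol Section 8 sets the target: "The primary objective is to estimate the incidence rate of malignancy, excluding non-melanoma skin cancer (NMSC), among adult UC patients". Section 9.3.5 then fixes the risk window for NMSC and malignancies. It gives the reason and the start in one sentence, "the occurrences of which are expected to be delayed relative to the time of exposure, the outcomes will be evaluated from drug initiation", and the end as "until the first event or loss to follow up, reflecting a 'once-exposed always at risk' paradigm".

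For Cohort 1, Section 9.3.4.2 defines the index date: "This will be the date of first prescription for tofacitinib since 30 May 2018". Cohorts 2 and 3 are also indexed on a first prescription, whereas Cohort 4 is indexed on the UC diagnosis. Section 9.3.5 has "end of data collection (30 June 2025) treated as censoring events".

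Section 9.7.2 provides one safeguard: "patients with a baseline history of malignancy will be excluded from the calculation of the incidence rate for malignancy". Section 9.3.1 takes malignancy history as ever, and Section 9.2.1.2 requires at least 12 months of prior enrollment.

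Section 9.7.2 also states: "This will be a time to first event analysis based on an index date defined for each cohort with appropriate censoring rules applied". It plans crude rates and cumulative incidence proportions. The strata named in Sections 9.7.2 and 9.7.4 do not include time since initiation. Section 7 gives the purpose: "Follow up of large cohorts of patients over a long period can help in the evaluation of any potential risk of malignancy".

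**The concern.** If an outcome is expected to appear late, the delay bears on both ends of the risk window. The protocol acts on it at one end only, which has two consequences.

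- **Numerator.** A cancer that was present at index but had not been diagnosed or coded, and is found in the following weeks or months, is counted as an event after exposure.
- **Denominator.** The first months of person-time enter in full, although a drug effect on cancer is least plausible then.

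The two can work in opposite directions. Early detection of existing disease raises the pooled rate. Early person-time without any drug effect dilutes a true later increase. One pooled rate cannot separate them.

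This matters because malignancy is the primary outcome, because Section 7 gives the evaluation of long-term risk as the purpose, and because the rates will stand next to those of three other cohorts. Diagnostic work-up around a UC diagnosis (Cohort 4) may differ from that around a treatment start (Cohorts 1-3), so the early excess need not be equal across cohorts.

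**Working it through.** **What the protocol allows to be checked.** It states no malignancy rate, follow-up distribution or event count, so there is no figure of its own to reproduce. The arithmetic below shows possible size under stated assumptions. It does not estimate the bias.

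**Input from the protocol.** The earliest index date is 30 May 2018 (Section 9.3.4.2) and data collection ends on 30 June 2025 (Section 9.3.5). Longest follow-up: T = 2,588 / 365.25 = 7.09 years.

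**Assumed inputs.** Entry is uniform over T. Loss of coverage is exponential with median m = 1.5, 2 or 3 years, so λ = ln 2 / m. The rate in the first L years after index is k times the later rate.

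**Step 1: share of person-time in the first L years.** Person-time at time t since index is proportional to exp(-λt)(1 - t/T). Integrating from 0 to T gives mean follow-up 1/λ - (1 - exp(-λT)) / (λ²T). The share S(L) is the integral from 0 to L divided by that total.

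| Median coverage | λ per year | Mean follow-up (years) | S(6 months) | S(12 months) | Share beyond 5 years |
|---|---|---|---|---|---|
| 1.5 years | 0.462 | 1.53 | 0.282 | 0.490 | 0.015 |
| 2 years | 0.347 | 1.81 | 0.245 | 0.436 | 0.024 |
| 3 years | 0.231 | 2.20 | 0.207 | 0.379 | 0.038 |

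**Step 2: unlagged rate divided by lagged rate.** With later rate r, the unlagged rate is r[kS + (1 - S)] and the lagged rate is r. The ratio is therefore 1 + (k - 1)S. For a 6-month lag:

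- k = 1: the ratio is 1.00 whatever S is.
- k = 1.5: from 1 + 0.5 × 0.207 = 1.10 to 1 + 0.5 × 0.282 = 1.14.
- k = 3: from 1 + 2 × 0.207 = 1.41 to 1 + 2 × 0.282 = 1.56.
- k = 0.5 (early rate half the later one): from 1 - 0.5 × 0.282 = 0.86 to 1 - 0.5 × 0.207 = 0.90. The pooled rate then understates the later rate.

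**Step 3: a wider range of coverage loss.** With loss of 0.10 to 0.50 per year, mean follow-up is 2.84 to 1.45 years. The first 6 months hold 17-29% of person-time and the first 12 months 31-51%. The 6-month ratio is 1.08-1.15 for k = 1.5 and 1.33-1.59 for k = 3.

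**Step 4: what in the protocol already addresses early cancers.**

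- The history exclusion (Sections 9.3.1 and 9.7.2) removes recorded cancers only. With a 12-month enrollment minimum, ever may mean one year of data for some patients.
- Of the two sensitivity analyses in Section 9.3.5, one concerns a switch within the 90-day window for acute events and the other concerns PML. Neither touches early cancers.
- Section 9.3.5 cites undiagnosed illness at the end of treatment as a reason for the 90-day extension. It has no counterpart at the start of exposure.
- Section 9.9 mentions trend analyses as optional, for tofacitinib patients only and in connection with channeling. It does not list latency as a limitation.

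**The case against.** The strongest reply is that the study is descriptive, with no a priori hypotheses (Section 9.1), and that the objective is a rate among initiators. A rate counted from initiation answers that objective, and expected delay is a sound reason to leave the end of the window open without moving the start. This stands: the day-0 rate is valid for what it is, and the protocol does not contradict itself.

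A second reply is that further analyses belong in the SAP, which is not at hand. Section 9.7 calls itself a brief overview, its strata are open-ended, and the checklist in Annex 2 refers details of the analysis plan to the SAP. This stands in part. One cannot say that no lagged analysis is planned anywhere. But the protocol itself sets the start rule for its primary outcome, so the start rule is open to comment here.

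A third reply is that cumulative incidence proportions are planned and could show timing. They could if given at several times since index, but Section 9.7.2 does not say so.

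Some stronger readings are tempting but unsupported:

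- **All cancers count, including those known before treatment.** They do not: recorded history is excluded, so a cancer found and coded in work-up before the index date does not count.
- **Early person-time dominates the rate.** With median coverage of 1.5-3 years the first 12 months hold 38-49% of person-time, and only the fastest loss in the wider range reaches 51%. For the first 6 months the share is at most 29%.
- **The primary rate is inflated by 10-56%.** That range rests on an assumed early excess for which the protocol gives no evidence.

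**Conclusion.** The point holds as a limited one. The start of the malignancy window is fixed at day 0 although the outcome is called delayed, and only recorded cancers are screened out. The resulting rate describes newly recorded first cancers after initiation. By itself it does not support statements on long-term or treatment-associated malignancy risk, or a side-by-side reading of cohorts with different index events.

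The direction is open and the size is unknown from the protocol. Under uniform entry and median coverage of 1.5-3 years, 21-28% of person-time lies in the first 6 months. The unlagged rate is 1.00 times the 6-month-lagged rate with no early excess, 1.10-1.56 times if the early detection rate is 1.5-3 times the later one, and below 1 if the early rate is lower. Coverage loss and the early-to-later ratio are both assumptions.

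**What to change.** In Sections 9.3.5 and 9.7.2, keep the day-0 analysis. Pre-specify beside it, for malignancy excluding NMSC, lung cancer, lymphoma and NMSC, in all four cohorts:

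- a 6-month-lagged rate that drops both the events and the person-time in the first 6 months after each index date, with a 12-month lag as sensitivity analysis;
- rates with events and person-years by time since index, for example under 6 months, 6 to under 12 months, 1 to under 2 years, 2 to under 4 years, and 4 years or more.

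State that conclusions on long-term malignancy risk will rest on the lagged rate and the later bands. Naming the lag in advance avoids choosing it after the data are seen, and the bands will themselves show whether an early excess exists.

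This needs an amendment sentence and some extra table rows from data already held. The price is fewer events and wider confidence intervals, most of all in the late bands: under the assumptions above, time beyond 5 years holds only about 1-4% of person-time.

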- Surgery for UC
- Death

For contextualization and risk characterization purposes, the incidence rates of the same safety events (listed in the primary and secondary objectives above) in adult UC patients initiating treatment with other approved systemic agents, as well as those patients naïve to biologics and immunomodulators/immunosuppressants will also be assessed. Therefore in total, incidence rates will be estimated within the following groups:

1. Cohort 1 (Tofacitinib cohort): UC patients initiating tofacitinib, overall and independently stratified by dose (5 mg twice daily, 11 mg once daily, 10 mg twice daily, 22 mg once daily) and prior biologic use (i.e. patients naïve to biologics vs. patients with prior biologic use)

Contextualization Cohorts:

- 2. Cohort 2 (Biologics cohort): UC patients who initiate biologics, with/without concurrent immunomodulators/immunosuppressants, overall and independently stratified by TNFi/non-TNFi use and number of previous biologic treatments
- 3. Cohort 3 (Immunomodulators/immunosuppressants cohort): UC patients who initiate immunomodulators/immunosuppressants (methotrexate [MTX], azathioprine [AZA], mercaptopurine [6-MP]) without concurrent biologics
- 4. Cohort 4 (Naïve cohort): UC patients naïve to both biologics and immunomodulators/immunosuppressants

Patients in the naïve cohort are expected to have milder disease relative to patients in the other 3 cohorts.

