Patients may switch between the tofacitinib and contextualization cohorts over time if inclusion/exclusion criteria listed below are met. Additionally, patients will be eligible for entry into a particular cohort each time they start a new therapy within the same drug class. For acute endpoints, patients will be censored from a particular cohort when they start a new therapy in a different drug class. For the endpoint of MACE, for example, patients in Cohort 1 (UC patients initiating treatment with tofacitinib) will be censored if and when they switch to a specific biologic agent, but will be eligible for subsequent inclusion into Cohort 2 (patients initiating treatment with biologics). For non-acute outcomes such as malignancy and death, outcomes will be evaluated using a "once exposed always at risk" paradigm (as described in Section 9.3.5).

Formal definitions of index dates/start of follow-up are provided in Sections 9.3.4.2 and 9.3.5.Details of exposure measurement (e.g., allowing specified gaps between prescriptions in continuous exposure, etc.) will be detailed in the statistical analysis plan (SAP).

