- 3. After December 2017, a patient whose first tofacitinib prescription occurred after a diagnosis of PsA (defined as either as having ≥ 1 inpatient or ≥ 2 outpatient PsA diagnosis codes on two unique calendar days, with at least one from a rheumatologist), OR
- 4. Between May 2018 and July 2019, a patient whose first tofacitinib prescription occurred after a diagnosis of UC (defined as the first UC diagnosis code from an inpatient visit or after the second UC diagnosis code from an outpatient visit), OR
- 5. After July 2019, a patient whose first tofacitinib prescription occurred after a diagnosis of UC (as defined above) AND after evidence of prior TNFi use (i.e. using all available data, a prescription for ≥1 TNFi agent prior to first tofacitinib prescription), OR
- 6. After September 2020, a patient aged ≥2 years whose first tofacitinib prescription occurred after a diagnosis of pcJIA (defined as either as having ≥ 1 inpatient or ≥ 2 outpatient pcJIA diagnosis codes on two unique calendar days, with at least one from a rheumatologist)

In contrast, off-label indications will be defined as use of tofacitinib among patients with other diagnoses (i.e. lack of diagnosis codes for RA, PsA, UC or JIA) not fulfilling any of the conditions outlined above. If off-label use among non-approved indications occurs, it is expected that tofacitinib will be more likely used among patients with other non-approved rheumatic conditions (e.g. psoriasis, ankylosing spondylitis) or other non-approved IBD conditions (e.g. Crohn's disease). Thus off-label indications will be identified by broadly targeting diagnosis codes for other non-approved rheumatic and IBD conditions. Additionally, if the indications for which tofacitinib is prescribed cannot be determined from the available data, these will be classified as unknown indications and will evaluated separately as described in Section 9.7.1.

Among patients with on-label indications, to facitinib dose will be assessed. For each of these patients, every to facitinib prescription will be classified as on-label or off-label based on the labeled dose for the patient's indication at the time of prescription. Thus, for the

purposes of this analysis, on-label dose of tofacitinib will be defined, based on each tofacitinib prescription, using the following criteria:

- 1. Between November 2012 and November 2017, a prescription of tofacitinib 5 mg twice daily occurring only after a diagnosis of RA (as defined above)

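### For malignancy, NMSC, UC surgery and death, the Cohort 2 and 3 contextualization rates include time after tofacitinib initiation and events also counted in Cohort 1

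*Protocol*

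**What the plan says.** Protocol section 8 sets the main aim: "The primary objective is to estimate the incidence rate of malignancy, excluding non-melanoma skin cancer (NMSC") in adult UC patients who start tofacitinib. It adds the rates "in adult UC patients initiating treatment with other approved systemic agents" (and in treatment-naïve patients) to put the tofacitinib rate in context. Section 9.1 states that there is no prior hypothesis.

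Section 9.2.1.2 allows patients to belong to more than one cohort: "Patients may switch between the tofacitinib and contextualization cohorts over time". What happens at a switch depends on the outcome:

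- **Acute outcomes.** "For acute endpoints, patients will be censored from a particular cohort when they start a new therapy in a different drug class".
- **Non-acute outcomes.** Section 9.2.1.2 says that "outcomes will be evaluated using a 'once exposed always at risk' paradigm". Section 9.3.5 applies this to malignancies, NMSC, UC surgery and death: "the outcomes will be evaluated from drug initiation until the first event or loss to follow up". It then adds: "If a patient switches to a new drug, the subsequent observation time will contribute to multiple therapies".

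Section 9.3.5 also plans a sensitivity analysis in which a new drug closes the risk window of the earlier one, but only for the 90-day window used for acute events. Section 9.7.3 promises on-drug as well as since-start rates in the interim reports, without saying which outcomes each applies to. Sections 9.7.2 and 9.7.4 set no such pair for the final report. Section 9.9 discusses channeling and misclassification of the 90-day window, but not overlap between cohorts.

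**The concern.** A contextualization rate is meant to show what happens in UC patients started on other systemic agents. Under the non-acute rule, the Cohort 2 and 3 rates are a mixture of time before tofacitinib and time after it. A cancer diagnosed after the move to tofacitinib is counted in Cohort 1 and in the earlier cohort.

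The protocol gives reason to expect such moves. Section 9.2.1.2.1 expects most UC patients on tofacitinib to have had other UC therapy first. In section 9.3.2, the on-label definition after July 2019 requires a UC diagnosis "AND after evidence of prior TNFi use".

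If tofacitinib raised malignancy risk, part of the excess would also sit in the rates it is read against, and the gap would usually look smaller than it is. In a safety study that is the less comfortable direction of error. The protocol plans a separating analysis for acute events but none for the primary outcome, so a reader of the final report could not tell how much of the context is shared.

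**Working it through.** The protocol states no expected rate, event count or precision target for malignancy, so there is no planned figure to reproduce. The check is the algebra of a mixed rate.

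**Inputs from the protocol (sections 9.2.1.2, 9.3.4.2 and 9.3.5).** No censoring at switch for these outcomes. Time after a switch counts for both drugs. Cohort entry from 30 May 2018 and end of data on 30 June 2025, so at most 7.09 years of follow-up.

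**Inputs that are assumptions.**
- r0: event rate in Cohort 2 or 3 before any tofacitinib.
- r1: event rate in Cohort 1, with R = r1/r0.
- rs: event rate of Cohort 2 or 3 patients after they start tofacitinib.
- f: share of Cohort 2 or 3 person-years that falls after tofacitinib initiation.

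**Step 1, general form.** Reported Cohort 2 or 3 rate = (1 − f)·r0 + f·rs. Apparent ratio = r1 / [(1 − f)·r0 + f·rs].

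**Step 2, switchers carry the Cohort 1 rate (rs = r1).** Apparent ratio = R / (1 − f + fR). Share of Cohort 2 or 3 events that are also Cohort 1 events = fR / (1 − f + fR). For R = 2 and f = 10%: 2/(0.9 + 0.2) = 1.82, and 0.2/1.1 = 18%.

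| True R | f = 5%: ratio (shared) | f = 10% | f = 20% |
|---|---|---|---|
| 1.5 | 1.46 (7%) | 1.43 (14%) | 1.36 (27%) |
| 2.0 | 1.90 (10%) | 1.82 (18%) | 1.67 (33%) |
| 3.0 | 2.73 (14%) | 2.50 (25%) | 2.14 (43%) |

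At R = 1 nothing moves. At R = 0.8 the ratio rises to 0.81, 0.82 and 0.83.

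**Step 3, what f might be.** As an illustration, assume uniform entry over 7.09 years, exponential loss of coverage (mean 3 years), and exponential time to tofacitinib (mean 1.5 years) in a fraction p of patients who would switch. With I(a) = 1/a − (1 − e^(−7.09a))/(7.09a²), f = p·[1 − I(1/3 + 1/1.5)/I(1/3)] = p·[1 − 0.859/1.850] = 0.536p.

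| p | f | True 2.0 appears as |
|---|---|---|
| 5% | 2.7% | 1.95 |
| 10% | 5.4% | 1.90 |
| 20% | 10.7% | 1.81 |
| 30% | 16.1% | 1.72 |

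On these assumptions, f = 20% needs p = 0.20/0.536 = 37%, so it lies towards the high end.

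**Step 4, does the direction always hold?** No. From step 1, with r1 above r0, the ratio falls only if rs exceeds r0. Take r1 = 1.5, r0 = 1.0, rs = 0.8 and f = 10%. The Cohort 2 rate is 0.9 + 0.08 = 0.98 and the ratio is 1.5/0.98 = 1.53, slightly away from 1.

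**The case against.** The strongest case on the other side has five parts.

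**This belongs in the SAP.** The protocol sends exposure details and methods to the SAP, which was not available for this review and may contain such an analysis. That limits the point but does not remove it. The protocol itself fixes the counting rule, and sets a separating analysis for acute events only. If the SAP already has one for these outcomes, a cross-reference is enough.

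**The primary estimate is untouched and no ratio is planned.** Both stand. A reader might infer that the primary malignancy rate is biased. It is not: Cohort 1 contains only tofacitinib initiators, and follow-up after a later drug is part of what an ever-exposed rate means. The ratios above are a yardstick for side-by-side reading, not a planned analysis.

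**The direction is not guaranteed.** This stands. A reader might infer that the overlap always pulls towards no difference, or that switching runs one way. Step 4 of the working shows an exception. Cohort 1 can include biologic-naïve patients, who may differ from switchers. The prior-TNFi condition defines on-label use and does not govern cohort entry, and the example in section 9.2.1.2 is a move from tofacitinib to a biologic. The condition also says nothing about immunomodulators, so f may well be smaller in Cohort 3.

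**The rule is deliberate.** Section 9.3.5 reasons that these events appear late after exposure. This also stands, and is why the planned rate should stay.

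**On-drug rates are promised.** They are promised for the interim reports only and are not tied to malignancy. The general reference in section 9.7.2 to censoring at therapy switches does not displace the outcome-specific rule in 9.3.5.

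**Conclusion.** The point holds for the contextualization rates. By the protocol's own rule, the Cohort 2 and 3 rates for malignancy, NMSC, UC surgery and death include tofacitinib-exposed person-time and events that Cohort 1 also counts, and no analysis in the protocol separates them. The planned Cohort 1 rate stands as it is.

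If switchers carry the Cohort 1 rate, a true ratio of 2.0 appears as 1.90 to 1.67 for f between 5% and 20%. The size rests wholly on f, which the protocol does not give. With little switching the effect is small: 1.95 at f = 2.7%. A shift towards 1 is the usual result when the two rates differ, but not a certain one. This is an inexpensive improvement to interpretation, not a flaw in the primary analysis.

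**What to change.** Keep the planned ever-exposed rate. In sections 9.3.5 and 9.7.2, for malignancy excluding NMSC, NMSC, UC surgery and death:

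1. Report, for Cohorts 2 and 3 separately, the person-years after tofacitinib initiation and the events that are also counted in Cohort 1. This measures f directly and shows whether the overlap matters.
2. Add a sensitivity analysis in which Cohort 2 and 3 follow-up ends at the first tofacitinib dispensing, shown beside the planned rate.

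A sentence in section 9.9 should name the overlap as a limitation.

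The cost is one further run and one table on data already held. The sensitivity analysis has its own weaknesses. Censoring at the start of tofacitinib may be informative, and it shortens follow-up. It also drops delayed cancers due to the earlier drug, which Cohort 1 would still count, so it can lower the Cohort 2 and 3 rates. It should therefore accompany the planned rate and not replace it.
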